# **4.3** Investigational product

The MONARCHTM Platform, Urology includes the MONARCHTM Tower, MONARCHTM Cart and MONARCHTM Controller, MONARCHTM Fluidics Pump, and Instruments and Accessories Kits. The MONARCHTM Platform, Urology enables electro-mechanical articulation and precise control of a flexible ureteroscope and/or a flexible mini-PCNL suction catheter ("catheter") for visualization and access to the urinary tract for diagnostic and therapeutic procedures. The ureteroscope and mini-PCNL suction catheter move only under continuous and direct physician control, via the MONARCHTM Controller. See Appendix IV for additional description of the system components.

## Off-the-Shelf Equipment Required for Study Procedure:

In order to complete the MONARCHTM Mini-PCNL procedure, the following off-the-shelf equipment, typically used in endourology procedures, will be required:

- Cystoscope, camera, light source, and tower
- Compatible Ureteral Access Sheath
- Laser Console and Compatible Laser Fiber
- Saline Bags
- Waste Management System
- Patient Drapes
- Ancillary disposables including but not limited to guide wires, single and dual lumen ureteral catheters, ureteral stents
- Ancillary operating room equipment including but not limited to C-arm, surgical bed, anesthesia machine, sterile drapes and tables, monitors

#### Device Labeling

A copy of the Instructions for Use (IFU) will be included with the devices.

#### **Device** Distribution

Device distribution for this study will be managed by Auris Health, Inc.

#### Device Accountability

Sponsor and Investigative Site will maintain device accountability as required for this Study.

#### Return of Materials Upon Study Termination

Unless other arrangements have been made, all components of the MONARCHTM Platform, Urology System will be returned to Auris Health, Inc. at the end of the study. This may include the return of all used MONARCHTM Ureteroscopy Kits and the MONARCHTM Mini-PCNL Suction Catheters for examination after every case.

# **5.** Criteria for Subject Selection and Withdrawal

Patients may withdraw from the study at any time, with or without reason and without prejudice to further treatment. In all cases of withdrawal, the reason(s) for withdrawal (if given) will be recorded upon study termination.

In addition, the investigator may withdraw the subject due to any of the following situations:

#### • Adverse event

- Any other reason determined by the investigator to be in the best interest of the subject
- Lost to follow-up
- Site termination
- Study termination
- Death

Subjects withdrawn from the Study prior to insertion of the sheath should be converted to conventional ureteroscopy or percutaneous nephrolithotomy. Subjects withdrawn due to an adverse event should be followed until the event has been resolved or is stable, if at all possible.

#### **5.1** Subject inclusion criteria

Pre-Procedure Inclusion Criteria	
 
Age ≥ 22 years
 
Simple renal caliceal and/or pyelo stone(s), ≥ 10 mm in size identified on CT scan, and appropriate for PCNL treatment according to AUA guidelines
 

	
 
Normal upper tract anatomy, amenable to PCNL and ureteroscopy
 

	4. BMI $< 40 \text{ kg/m2}$
	5. Patients with a percutaneous tract length < 15cm as measured by the estimation of the skin to stone or skin to appropriate calyx for treatment through a CT scan
	6. Patient is an appropriate candidate for a mini-PCNL based on the clinical guidelines and investigator assessment.

## **5.2** Subject exclusion criteria

Pre-Procedure Exclusion Criteria	Subjects will be excluded from participating in this study if they meet any of the following criteria prior to initiation of the procedure:
	1. Any medical or physical condition/limitation that would contra- indicate a conventional ureteroscopy or PCNL (e.g., atypical interposition of visceral organs (bowel, spleen, or liver)) in the supine position. This assessment will be made by the investigator team.
	
 
Participation in any other clinical trial 30-days before and throughout the duration of the study that might impact the results
 

	3. A solitary functioning kidney
	4. Female subjects who are pregnant or nursing or those of child-
	bearing potential refusing a pregnancy test
	5. Presence of ureteral impacted stones
	6. Presence of ureteral obstruction
	7. Presence of untreated urinary tract infection, urosepsis
	8. Inability to give consent
	9. Presence of a renal mass which has not been investigated
Printed copie	s are considered UNCONTROLLED documents after the date printed. Printed on September 17, 2024.

#### CONFIDENTIAL, PROPRIETORY OF AURIS HEALTH, INC

First-in-Human Study Protocol – Monarch Urology Rev: C	PROTOCOL	Doc #:	104-010990-00
	First-in-Human Study Protocol – Monarch Urology	Rev:	С
(Protocol No.: 2021-URO-0001) Page: 24 of 48	(Protocol No.: 2021-URO-0001)	Page:	24 of 48

 
Staghorn stone
 
Patient has an electrically or magnetically activated implanted medical device
 
Significant pharmacological anticoagulant therapy or uncorrected
 

bleeding diathesis 13. Tumor in the probable access tract area and potential malignant renal tumor

In addition, subjects will be excluded from participating in this Study if any of the following exclusion criteria occur during the endoscopic procedure.

Intra-Procedure Exclusion Criteria	Any presenting condition discovered intra-procedurally that in the opinion of the investigator would make participating in this study not in the patient's best interest. For example,
	patients no longer considered good candidates for a mini- PCNL procedure for the removal of the kidney stones.

Criteria identified intraoperatively to justify patient exclusion, will be reviewed by the Sponsor, and considered for articulation directly in the protocol for future cases to ensure consistency in exclusion.

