expected to take up to 16 weeks and includes a 30-day follow-up visit for each enrolled participant.Primary EndpointThe primary endpoint is the completion of the robotic-assisted mini-PCNL kidney stone removal procedure including: • Gaining safe concomitant (i.e., retrograde and antegrade) access to the upper urinary tract • Locating and visualizing kidney stones • Enabling fragmentation of stones by standard of care method • Evacuating stone fragments and dustSafety EndpointsThe following will be considered secondary endpoints: • Adverse events through 30-days post-operative, scored on the Clavien-Dindom	Site		
stone removal procedure including:         • Gaining safe concomitant (i.e., retrograde and antegrade) access to the upper urinary tract         • Locating and visualizing kidney stones         • Enabling fragmentation of stones by standard of care method         • Evacuating stone fragments and dust         Safety Endpoints         • Adverse events through 30-days post-operative, scored on the Clavien-Dindom	Duration of Study	expected to take up to 16 weeks and includes a 30-day follow-up visit for each	
Adverse events through 30-days post-operative, scored on the Clavien-Dindo	Primary Endpoint	
 
stone removal procedure including:
 
Gaining safe concomitant (i.e., retrograde and antegrade) access to the upper urinary tract
 
Locating and visualizing kidney stones
 
Enabling fragmentation of stones by standard of care method
 
	

 
Conversion to conventional treatment methods
 
	Safety Endpoints	
 
Adverse events through 30-days post-operative, scored on the Clavien-Dindo scale
 
	
Follow-Up Schedule Each enrolled subject will be followed up to 30 days ±7 days post procedure.	Follow-Up Schedule		

PROTOCOL	Doc #:	104-010990-00
First-in-Human Study Protocol — Monarch Urology	Rev:	С
(Protocol No.: 2021-URO-0001)	Page:	8 of 48

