#### Study Exit

Once the subject has completed 30  $(\pm 7)$  days follow-up or has withdrawn, they should be exited from the Study provided they do not have any conditions that require continued follow-up. The date of exit and subject status will be recorded on the Study Completion Form.

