The Investigator should follow all unresolved serious adverse events until the events are resolved or stabilize, the subject is lost to follow-up, the subject has withdrawn consent, or the adverse event is otherwise explained.

For purposes of this study, the following events are not likely to be device-specific adverse events, since they are known procedure/anesthesia related adverse events:

- Any pre-planned surgical procedures
- Urethral false passage and long-term urethral stricture
- Various grades ureteral injury leading to perforation, avulsion, intussusception, and long-term stricture due to retrograde access
- Vesicoureteral reflux
- Uretero-iliac fistula
- Extra-renal stone migration
- Visceral injury due to percutaneous access that may require secondary intervention
- Renal pseudo-aneurysm
- Arterio-venous fistula
- Retro-peritoneal or perirenal fluid collection: urinoma, hematoma
- Perforation of renal pelvis
- Major bleeding
- Urinary Infection or sepsis
- Ureteral stent migration, forgotten stent

Printed copies are considered UNCONTROLLED documents after the date printed. Printed on September 17, 2024.

CONFIDENTIAL, PROPRIETORY OF AURIS HEALTH, INC

- Post-operative upper-tract obstruction
- Post decompression hyper-diuresis
- Renal Fracture

This listing of events is intended to provide guidance to the investigational the site for purposes of adverse event reporting. The Investigator at the investigational site should utilize his/her own clinical judgment in evaluating adverse experiences and may decide that the above events should be reported as device-specific adverse events.

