1.2 Study Design

This is a single-center, prospective, single-arm study to collect descriptive data on the roboticassisted mini-PCNL removal of kidney stones using the MONARCH[™] system.

The study will enroll up to 20 patients. Each enrolled subject will be followed up to 30 days \pm 7 days post procedure.

2 Treatment Assignment

This is a single-arm study where all enrolled subjects will have the MONARCH[™] system utilized for removal of kidney stones via a mini-PCNL procedure.

3 Randomization and Blinding Procedures

As this is a single-arm study, no randomization occurred, and no blinding procedures are required.

4 Interval Windows

Interval windows for the purpose of analysis in this study are not defined outside of those already specified in the protocol for visit scheduling where the collection of data for the primary and safety endpoints occurs.

Table 1 Schedule of Assessments in the protocol specifies the following visit windows:

- Screening/baseline: approximately 30 days prior (allowing up to 60 days prior) to the procedure
- Pre-operative imaging, no longer than 30 days pre-procedure
- Post-operative 30 days follow-up (± 7 days)

Any information entered in the electronic Case Report Forms (eCRFs) at a given visit will correspond to the scheduled visit. There will be no assigning of observations to time points outside of the visit to which they are recorded in the eCRFs.

5 Levels of Significance

No hypotheses are specified for this study and no p-values are being calculated, therefore no level of significance is specified. All estimation of endpoints will be performed using 95% confidence intervals where indicated below.

6 Analysis Sets

The summary of all performance and safety endpoints will be performed on the set of subjects in whom the MONARCHTM system is utilized during the procedure. This will be labeled as the Full Analysis Set (FAS) and will be identified by having a time recorded in the "When was the Ureteroscope introduced (timestamp)?" field on the Procedure: Ureteroscopy and Percutaneous Access eCRF.

7 Sample Size Justification

The study is expected to enroll up to 20 subjects. No formal hypothesis is being tested and therefore the sample size determination is not based on a statistical power calculation, but rather is deemed sufficient for a descriptive summary of safety and primary endpoints in this first-in-human experience with the study device.

8 Analyses to be Conducted

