8.10 Handling of Missing Data

All summaries will be performed only on subjects undergoing the scheduled procedure and only observed data will be summarized. There will be no imputation of data for early terminated subjects or for missing data within the database.

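### Subjects excluded or withdrawn mid-operation after the MONARCH ureteroscope is in can be exited without the 30-day visit, so late adverse events can go unrecorded

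*Protocol*

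**What the plan says.** **Leaving the study.** Protocol 5.2 (Intra-Procedure Exclusion Criteria) states that "subjects will be excluded from participating in this Study if any of the following exclusion criteria occur during the endoscopic procedure". The criterion is any condition found during the procedure that, in the investigator's opinion, makes participation contrary to the patient's interest. Nothing is said about follow-up afterwards. Protocol 5 separately lets the investigator withdraw a subject for an adverse event or on best-interest grounds. Under Study Exit (Protocol 4.2), a subject who has completed the 30 (±7) day follow-up "or has withdrawn, they should be exited from the Study provided they do not have any conditions that require continued follow-up".

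**Safeguards.** Protocol 5: "Subjects withdrawn due to an adverse event should be followed until the event has been resolved or is stable, if at all possible". Protocol 8.1: "The Investigator should follow all unresolved serious adverse events until the events are resolved or stabilize". Protocol 5 also says: "Subjects withdrawn from the Study prior to insertion of the sheath should be converted to conventional ureteroscopy or percutaneous nephrolithotomy". It does not say which sheath is meant.

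**Follow-up promised.** The synopsis states: "Each enrolled subject will be followed up to 30 days ±7 days post procedure". SAP 1.2 repeats this. The synopsis entry on study duration includes a 30-day visit for every enrolled participant, and Protocol 4.2 (Follow-up) gives each subject one follow-up visit.

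**Analysis.** The safety endpoint in Protocol 7 is adverse events through 30 days, graded by Clavien-Dindo. SAP 6 puts a subject in the FAS once a ureteroscope introduction time is recorded. SAP 8.10 limits summaries to subjects who undergo the scheduled procedure, says "only observed data will be summarized", and rules out imputation. SAP 8.12 plans no sensitivity analysis.

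**The concern.** The exit wording treats the end of robotic treatment as the end of study participation. A subject can have had the ureteroscope driven in the kidney, and possibly the guided needle passed, and then be released with no 30-day assessment. Protocol 8.1 lists harms that can plausibly appear after the day of surgery, such as pseudo-aneurysm, arterio-venous fistula, urinoma and sepsis.

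Two things are at stake. The first is completeness of an endpoint defined through day 30. The second is the direction of any error: an operation stopped early is plausibly a harder one, so the missing follow-up need not be a random sample. If these subjects stay in the denominator with no late event recorded, the reported proportion can only be too low. With at most 20 subjects, one or two of them can change how the safety table reads.

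**Working it through.** There is no stated figure to reproduce. The sample size was not statistically derived (Protocol 9.4, SAP 7), so the check is mainly a reading of the rules.

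**Step 1: order of exposure.** Protocol 4.2 (description of the procedure) runs: ureteral access sheath by conventional cystoscopy, MONARCH ureteroscope, electromagnetically guided needle, tract dilation with the percutaneous sheath. FAS membership begins at the second step.

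**Step 2: which rule governs a subject stopped after that step?**
- *Stopped because of an adverse event.* Protocol 5 requires follow-up until that event resolves or stabilises, where possible. Protocol 8.1 covers unresolved serious events, and the Study Exit proviso blocks release while a condition needs follow-up. The event is captured. New events after it stabilises, but before day 30, are not clearly covered.
- *Stopped with no adverse event evident*, for example because the patient is no longer a good mini-PCNL candidate. None of the three safeguards clearly applies. If exclusion is handled as withdrawal, which the best-interest ground in Protocol 5 supports, Study Exit releases the subject.
- *The sheath sentence in Protocol 5.* If it means the percutaneous sheath, it reaches exposed subjects but speaks only of conversion. If it means the ureteral sheath, those subjects are unexposed, and withdrawal after exposure without an adverse event has no provision. Neither reading secures the visit.

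**Step 3: which denominator?** SAP 6 includes these subjects. The SAP 8.10 restriction to those undergoing the scheduled procedure leaves it unclear whether a stopped case is summarised. SAP 8.8 monitors adverse events to the end of follow-up, which is not defined for an excluded subject.

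**Step 4: size, by assumption.** Take an FAS of n = 20, the planned maximum. Let m subjects lack day-30 data, with m = 1 to 4 assumed, and suppose no event of the type of interest is seen in the rest. Each subject is 1/20 = 5 percentage points. Exact (Clopper-Pearson) limits: for 0/n the upper limit is 1 − 0.025^(1/n), so 0/20 gives 1 − 0.025^(1/20) = 16.8%. For x > 0 the limits are the 2.5% quantile of Beta(x, n − x + 1) and the 97.5% quantile of Beta(x + 1, n − x).

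| m | Followed subjects only (upper limit) | Unseen counted as no event (upper limit) | All unseen had an event (95% CI) |
|---|---|---|---|
| 1 | 0/19 (17.6%) | 0/20 (16.8%) | 1/20 = 5% (0.1–24.9%) |
| 2 | 0/18 (18.5%) | 0/20 (16.8%) | 2/20 = 10% (1.2–31.7%) |
| 3 | 0/17 (19.5%) | 0/20 (16.8%) | 3/20 = 15% (3.2–37.9%) |
| 4 | 0/16 (20.6%) | 0/20 (16.8%) | 4/20 = 20% (5.7–43.7%) |

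If each subject has probability q of such an exit, the chance of at least one in 20 is 1 − (1 − q)^20: 64%, 88%, 96% and 99% for q = 5%, 10%, 15% and 20%. These values of q are also assumptions.

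**The case against.** A reader might infer that the 30-day data go missing in the cases that went worst. The documents do not support that. The safeguards in Protocol 4.2 (Study Exit), 5 and 8.1 should record and grade an event that stops the operation.

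Three further inferences also fail:
- *That bleeding, difficult puncture or poor vision triggers exclusion.* Protocol 5.2 names none of these. Informative loss is plausible, not shown.
- *That conversion means leaving the study.* Conversion is a counted safety endpoint, and no passage makes it an exit on its own.
- *That patients lose clinical surveillance.* Protocol 2.1 (Radiation) describes the post-operative CT as standard of care, and Protocol 13 says clinical follow-up is not influenced by enrolment. What can be lost is study data.

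The defence can add that SAP 8.2 already tabulates completed and discontinued FAS subjects with reasons, so early exits would be visible. It can also say that SAP 8.8 specifies counts and percentages without intervals, and only listings if fewer than five adverse events are reported. The intervals above therefore illustrate size and are not planned output. The phrase on following subjects up to 30 days can also be read as a ceiling.

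Most of this stands and narrows the point. The conflict remains, because the synopsis and the Follow-up paragraph of Protocol 4.2 provide the visit in firmer terms. A discontinuation table does not show for whom adverse events were ascertained to day 30.

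**Conclusion.** The point holds in a limited form. As written, the exclusion and exit rules allow a device-exposed subject to leave without the 30 (±7) day visit, contrary to the general follow-up statements. The loss is confined to subjects stopped with no adverse event evident and to later events after a recognised one has stabilised.

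The downward bias depends on the FAS being the denominator, which SAP 6 indicates and SAP 8.10 leaves unsettled. Its size rests on an assumed count: up to 5 percentage points per subject, or 5 to 20 points for one to four of 20. The upper end requires that every unseen subject had an event.

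The primary endpoint and conversion are unaffected, since both concern the procedure itself and come from the Investigator Assessment. In a descriptive feasibility study without hypotheses, this should be fixed but does not undermine the main result.

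**What to change.** - **Protocol 4.2, 5 and 5.2.** Reconcile these with the synopsis, the Follow-up paragraph of Protocol 4.2 and SAP 1.2, so that stopping the robotic procedure is distinct from leaving the study. Every subject with a ureteroscope introduction time keeps adverse-event collection and the scheduled 30 (±7) day visit unless consent is withdrawn. The investigator's intra-operative decisions stay as they are.
- **Protocol 5.** State which sheath the conversion sentence refers to.
- **SAP 8.10.** Align the population wording with the FAS in SAP 6.
- **SAP 8.8.** Report the number of FAS subjects with adverse events ascertained to day 30, and a worst-case bound that counts those without ascertainment as having an event.

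The cost is some wording, one table line and at most a few visits already in the Schedule of Assessments. SAP 8.9 and 9 describe parts of conduct in the past tense. If enrolment has ended, the SAP changes can still be made.

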# **6.** Treatment of subjects

The MONARCHTM Platform, Urology and its accessories are intended to access and visualize anatomical locations within the urinary tract and interior of the kidney for diagnostic and therapeutic procedures via transurethral or transurethral in conjunction with percutaneous access routes. The use of this device to treat kidney stones is previously described in this protocol in Section 4.3.

# 7. Assessment of Endpoints

#### **Primary Endpoint**

The primary endpoint is the successful completion of the robotic-assisted kidney stone removal procedures including:

- Gaining safe concomitant (i.e., retrograde and antegrade) access to the upper urinary tract
- Locating and visualizing the kidney stones
- Enabling fragmentation of stones by standard of care method
- Evacuating stone fragments and dust

The above bulleted device endpoints will be assessed regardless of procedural outcome (e.g., evacuation of stone fragments and dust may still be achieved by the device even if the patient is not stone free).

#### Safety Endpoints

The following will be considered safety endpoints:

- Adverse events through 30-days post-operative, scored on the Clavien-Dindo scale
- Conversion to Conventional Treatment Methods

Adverse events: Adverse events that may have been caused by any component of the procedures including those related to the MONARCHTM Platform, Urology System and/or Components.

Clavien-Dindo scale: Clavien-Dindo system for grading the severity of postoperative complications. See Appendix III.

Conversion to Conventional Treatment Methods: Number of procedures converted to the conventional ureteroscopy or percutaneous nephrolithotomy for any reason.

# **8.** Assessment of safety

## **8.1** Adverse Events

All adverse events (AE) and serious adverse events (SAE) will be monitored once patient is enrolled through the end of follow-up.

An AE is defined as any undesirable clinical occurrence in a patient whether or not it is considered to be device related. In addition, the definition of AE applies to any event with an onset post study procedure or to any underlying diseases, present at baseline, that exacerbate in severity post study procedure. Therefore, an underlying disease that was present at the time of enrollment is not reported as an AE, but any increase in the severity of the underlying disease is to be reported as an AE. All reported AEs must be recorded in the database. A description of the event, including the start date, resolution date, action taken, and the outcome should be provided, along with the Investigator's assessment of the relationship between the AE, the study treatment, and the study procedure.

The following definitions for rating severity of adverse events will be used:

- Mild: Awareness of signs or symptoms, but easily tolerated; are of minor irritant type; causing no loss of time from normal activities; symptoms would not require medication or a medical evaluation; signs or symptoms are transient.
- Moderate: Interferes with the subject's usual activity and/or requires symptomatic treatment.
- Severe: Symptom(s) causing severe discomfort and significant impact of the subject's usual activity and requires treatment.

A serious adverse event (SAE) is defined as an event which leads to any of the following:

- Death
- Life-threatening illness or injury
- A permanent impairment of a body structure or a body function
- Requires in-patient hospitalization or prolongation of existing hospitalization
- Resulted in medical or surgical intervention to prevent life-threatening illness or injury or permanent impairment to a body structure or a body function
- Led to a fetal distress, fetal death, or a congenital abnormality or birth defect

Each AE will be evaluated on its relatedness (Not Related, Possible, Probably, Causal) to both the study device and study procedure, according to the following definitions:

- Not related: Relationship to the device or procedure can be excluded when:
  - the event has no temporal relationship with the use of the investigational device, or the procedures related to application of the investigational device;
  - the adverse event does not follow a known response pattern to the medical device (if the response pattern is previously known) and is biologically implausible;
  - the discontinuation of medical device application or the reduction of the level of activation/exposure when clinically feasible -
  - and reintroduction of its use (or increase of the level of activation/exposure), does not impact on the adverse event;
  - the event involves a body-site or an organ that cannot be affected by the device or procedure;
  - the adverse event can be attributed to another cause (e.g. an underlying or concurrent illness/ clinical condition, an effect of another device, drug, treatment or other risk factors);
  - Harms to the subject are not clearly due to use error; or

In order to establish the non-relatedness, not all the criteria listed above might be met at the same time, depending on the type of device/procedure and the adverse event.

- **Possible:** The relationship with the use of the investigational device or comparator, or the relationship with procedures, is weak but cannot be ruled out completely. Alternative causes are also possible (e.g. an underlying or concurrent illness/ clinical condition or/and an effect of another device, drug or treatment). Cases where relatedness cannot be assessed, or no information has been obtained should also be classified as possible.
- **Probable:** The relationship with the use of the investigational device or comparator, or the relationship with procedures, seems relevant and/or the event cannot be reasonably explained by another cause.
- **Causal:** The serious adverse event is associated with the investigational device, comparator or with procedures beyond reasonable doubt when:
  - The event is a known side effect of the product category the device belongs to or of similar devices and procedures;
  - The event has a temporal relationship with the device uses/application or procedures;
  - The event involves a body-site or organ that:
    - The device or procedures are applied to or is adjacent to;
    - The device or procedures have an effect on;
  - The event follows a known response pattern to the medical device (if the response pattern is previously known);
  - The discontinuation of medical device application (or reduction of the level of activation/exposure) and reintroduction of its use (or increase of the level of activation/exposure), impact on the event (when clinically feasible);
  - O Other possible causes (e.g. an underlying or concurrent illness/clinical condition and/or

Printed copies are considered UNCONTROLLED documents after the date printed.

Printed on September 17, 2024. CONFIDENTIAL, PROPRIETORY OF AURIS HEALTH, INC

Pr.	PROTOCOL	Doc #:	104-010990-00
	First-in-Human Study Protocol – Monarch Urology	Rev:	С
	(Protocol No.: 2021-URO-0001)	Page:	27 of 48

an effect of another device, drug, or treatment) have been adequately ruled out; Harm to the subject is due to error in use

In order to establish the relatedness, not all the criteria listed above might be met at the same time, depending on the type of device/procedures and the serious adverse event.

An adverse event is considered to be non-device-related and non-procedure-related when, in the judgment of the Investigator, it is reasonable to believe that the event is neither associated with the use of the MONARCHTM Platform, Urology nor the study procedure (other products, surgical techniques, or medications required specifically for the procedure). Examples of these non-device-related and non-procedure related Adverse Events are related to concomitant medications (e.g. bleeding associated with anticoagulation medication) or a subject's pre-existing condition. Pre-existing conditions that are aggravated or become more severe during or after the procedure should be evaluated on a case-by-case basis to determine if the event may be more appropriately classified as device-related or procedure-related.

Site PI will be responsible for identifying adverse events during the procedure and during the standard of care follow-up period. Site PI will review adverse events experienced by subjects treated at their site during the procedure standard of care follow-up period and will record them in the medical record. Site PI will review all adverse events, expected or unexpected, per standard medical care.

Site PI will classify AEs as expected or unexpected, and report AEs directly to the Sponsor and IRB per local reporting policy. The lead investigator will capture all AEs occurring at the site including unanticipated AEs, in the electronic data capture instrument. Sponsor or its designee, may assist the Investigator in determining potential reportability to the FDA and other regulatory authorities as an Unanticipated Adverse Device Effect (UADE).

The Investigator should follow all unresolved serious adverse events until the events are resolved or stabilize, the subject is lost to follow-up, the subject has withdrawn consent, or the adverse event is otherwise explained.

For purposes of this study, the following events are not likely to be device-specific adverse events, since they are known procedure/anesthesia related adverse events:

- Any pre-planned surgical procedures
- Urethral false passage and long-term urethral stricture
- Various grades ureteral injury leading to perforation, avulsion, intussusception, and long-term stricture due to retrograde access
- Vesicoureteral reflux
- Uretero-iliac fistula
- Extra-renal stone migration
- Visceral injury due to percutaneous access that may require secondary intervention
- Renal pseudo-aneurysm
- Arterio-venous fistula
- Retro-peritoneal or perirenal fluid collection: urinoma, hematoma
- Perforation of renal pelvis
- Major bleeding
- Urinary Infection or sepsis
- Ureteral stent migration, forgotten stent

Printed copies are considered UNCONTROLLED documents after the date printed. Printed on September 17, 2024.

CONFIDENTIAL, PROPRIETORY OF AURIS HEALTH, INC

- Post-operative upper-tract obstruction
- Post decompression hyper-diuresis
- Renal Fracture

This listing of events is intended to provide guidance to the investigational the site for purposes of adverse event reporting. The Investigator at the investigational site should utilize his/her own clinical judgment in evaluating adverse experiences and may decide that the above events should be reported as device-specific adverse events.

